Table 2 Schedule of Activities: Preliminary Food Effect Assessment, Part 1B	Note for fresh paired tumor biopsies was updated	Updated for clarity.
1.3.3 Parts 1A and 1B – Pharmacokinetic, ECG, and CCI Sampling Schedule	Visit window on Day 8 was deleted. PK sampling footnote was updated.	For consistency with Table 1.
Table 3 Part 1A M4076 Monotherapy Dose Escalation: Pharmacokinetic, ECG and CCI		

Section # and Name	Description of Change	Brief Rationale
2.3 Benefit/Risk Assessment	Added new identified and important potential risks (rash and hypersensitivity, respectively).	Based on the new available clinical data from this study, new risks have been added.
	Risk associated with DDI information was updated.	Based on the DDI assessment using in vitro data.
4.1 Overall Design	Flexible wording added for Part 1B of the study.	Updated for clarity and flexibility.
5.2 Exclusion Criteria	Updated prior/concomitant therapy criterion.	Based on the DDI assessment using in vitro data.
6.5.3 Prohibited Medicines	Risk associated with DDI information was updated.	Based on the DDI assessment using in vitro data.
6.6.2.1 Dose Interruptions and Modifications	Added new identified and important potential risks (rash and hypersensitivity, respectively).	Based on the new available clinical data from this study, new risks have been added.
	Table 10 updated with 300 mg related information.	Updated for completeness.
8.2.2 Vital Signs	Semi-supine changed to semi-recumbent.	Updated for consistency with eCRF design.

CCI

9.2 Sample Size Determination	Updated number of participants to 40 in Part 1A.	To recruit additional cohorts, if needed.
9.4.2 Safety Analyses	Deleted interim analysis from Part 1A.	Updated for clarity.
9.4.4 Sequence of Analyses	Primary analysis will be done only for dose escalation part of the study.	Updated for clarity.
Appendix 13 Protocol Amendment History	Update related to V 3.0 copied to this section.	Updated for completeness.
Throughout	Minor editorial and document formatting revisions.	Minor; therefore, have not been summarized.

DDI = drug-drug interaction; ECG = electrocardiogram; eCRF = electronic case report form.

- Confidential -

1.1 Synopsis

Protocol Title: A First-in-human, Phase 1, Open-label Study of the ATM inhibitor M4076 in Participants with Advanced Solid Tumors

Short Title: First-in-human Study of M4076 in Advanced Solid Tumors

Rationale: The purpose of this study is to establish the safety, tolerability and pharmacokinetic (PK) profile (with and without food), maximum tolerated dose (MTD; if observed) and recommended dose for expansion (RDE) for M4076 in patients with advanced solid tumors for which no standard therapy is available.

Objectives and Endpoints:

The following table summarizes the objectives and estimands of the study.

Objectives and Estimands: M4076 Monotherapy Dose Escalation (Part 1A) and Preliminary Food Effect Assessment (Part 1B)

Objectives	Estimands attributes
Primary	

To determine dose-toxicity relationship and MTD (if reached) of M4076 monotherapy in patients with advanced solid tumors
	
Endpoints:
 
 Occurrence of Dose Limiting Toxicities (DLTs). Occurrence of adverse events (AEs) and treatment-related AEs. Occurrence of clinically significant changes in vital signs, laboratory parameters, and 12-lead electrocardiogram (ECG) findings. 
Strategy for handling intercurrent events:
 
For DLTs:
 
 Discontinuation of treatment (> 20% planned treatment missed during DLT period) to prevent a DLT: composite strategy (to be considered a DLT) Discontinuation of treatment administrations not due to DLT or preventing a DLT (> 20% of planned treatment missed during DLT period): participant not considered in DLT analysis. 
For other endpoints:
 
All available data from participants in safety analysis set will be used.
 
Population:
 
Patients with advanced solid tumors, who are intolerant or have no effective standard therapies available to them.
 
Population level summary:
 
 DLT probability as estimated using BLRM and credibility interval (only applicable for DLTs). Standard summary statistics.
Secondary	

To determine the recommended dose for expansion (RDE) of M4076 monotherapy in participants with advanced solid tumors
	
 In addition to safety and tolerability, changes from baseline for the following Pd biomarkers may be considered for determining the RDE: ATM pathway readouts such as, but not limited to, p-ATM, γ-H2AX and p-CHK2 in blood and tumor. In addition, pharmacokinetic (PK) data will be used to support determination of the RDE.

To characterize the PK profile of M4076 monotherapy in participants with advanced solid tumors
	
 PK parameters of M4076 in plasma after single dose and multiple doses. Urine PK parameters (e.g., renal clearance) will be characterized in Part 1B data permitted.

Objectives	Estimands attributes
To evaluate preliminary clinical activity parameters of M4076 monotherapy in participants with advanced solid tumors	Endpoints 
 Objective response (OR) according to RECIST 1.1 assessed by Investigator. Duration of response (DoR) according to RECIST 1.1 assessed by Investigator. Progression Free Survival (PFS) according to RECIST 1.1 assessed by Investigator.
To assess the effect of food on the PK of M4076 administered as a single dose under fed/fasting conditions in a cohort of participants with advanced solid tumors at the RDE from Part 1A.	Endpoints Fed/fasted ratio of M4076 plasma PK parameters: $AUC_{0-tlast}$, $AUC_{0-\infty}$ and, C_{max} when administered as a single dose with or without food.
To assess changes in pharmacodynamic markers of M4076 activity in tumor and blood during M4076 monotherapy	Endpoints Absolute and relative changes over time from baseline of ATM pathway readouts, such as, but not limited to p-ATM, p-CHK2 and γ -H2AX.

AE = adverse event; ATM = ataxia-telangiectasia mutated; AUC = area under the concentration-time curve; BLM = Bayesian 2-parameter Logistic Regression Model; DLT = dose limiting toxicity; DoR = duration of response; ECG = electrocardiogram; γ -H2AX = gamma histone family member X; MTD = maximum tolerated dose; OR = objective response; Pd = pharmacodynamics; p-ATM = phosphorylated ataxia-telangiectasia mutated; p-CHK2 = checkpoint kinase 2 protein; PFS = progression free survival; RECIST = Response Evaluation Criteria in Solid Tumors; RDE = recommended dose for expansion.

Overall Design: This is an open-label, Phase 1, clinical study of M4076. Part 1A is a M4076 monotherapy dose escalation designed to determine the safety, tolerability, PK, pharmacodynamics and early signs of efficacy in participants with solid tumors. Once an RDE is declared in Part 1A, a preliminary food effect cohort, Part 1B, may follow and will be conducted at the RDE or a lower dose than RDE determined from Part 1A. Part 1B is a randomized, 2-sequence, 2-period, cross-over design.

Disclosure Statement: This is an unblinded sequential treatment study with 2 parts: dose escalation (Part 1A) and food effect study (Part 1B).

Number of Arms: Not applicable.

Blinding: No blinding

Number of Participants: Approximately 40 participants are planned to be assigned to study intervention, including 22 to 28 participants in Part 1A (planned 4 potential dose levels) and 12 participants in Part 1B; the sample size for the MTD and/or RDE dose level needs to be at least 6 participants.

Study Intervention Groups and Duration: It is estimated that participants will be on the study for an approximate duration of 105 days/15 weeks.

[figure not shown]
Involvement of Special Committee(s): Safety Monitoring Committee.

1.2 Schema

[Figure 1](#) presents a study schema overview of the study.

- Part 1A: Dose escalation of M4076 monotherapy ([Figure 2](#)).
- Part 1B: Preliminary food effect cohort will follow at the recommended dose for expansion (RDE) established in Part 1A.

[figure not shown]
[Figure 1](#) Study Schema Overview

The cohort size planned in Part 1A is 3 participants per Dose Level (DL). The proposed DLs represented in [Figure 2](#) may be adjusted based on Safety Monitoring Committee (SMC) decision to reach exposures associated with preclinical efficacy while balancing safety and tolerability.

After maximum tolerated dose (MTD) and/or RDE have been determined in Part 1A, an additional cohort of 12 participants may be enrolled in Part 1B at this dose to assess preliminary effect of food on M4076 monotherapy.

[Figure 2](#) Part 1A - M4076 Monotherapy Dose Escalation Schema

Note: A DL of 300 mg was also administered orally once daily.

DL = dose level; MTD = maximum tolerated dose; RDE = recommended dose for expansion; SMC = safety monitoring committee.

1.3 Schedule of Activities

The Schedule of Activities for Part 1A (M4076 Monotherapy Dose Escalation) daily dosing schedule of this study is provided in [Table 1](#). Additional assessments may be performed at unscheduled time points if clinically indicated at the Investigator's discretion. To facilitate timely administration of study intervention, safety laboratory samples may be obtained up to 3 days before dosing. If laboratory samples are drawn before the day of dosing, they should be recorded in the case report forms (CRF) corresponding to the day of planned M4076 administration. The Part 1A pharmacokinetic (PK), electrocardiogram (ECG) and pharmacodynamic (Pd) biomarker assessments schedule is detailed in [Table 3](#).

The Schedule of Activities for Part 1B (preliminary Food Effect Assessment) is provided in [Table 2](#). The Part 1B PK, ECG, and Pd biomarker assessments schedule is detailed in [Table 4](#).

For Part 1A, potential variations in study intervention schedules and schedule of activities due to alternative dosing schedules are found [Appendix 7](#). Please see Sections [4.1.1](#) and [4.1.2](#), and [Appendix 12](#) for details on model for Bayesian dose escalation.

1.3.1 Part 1A – M4076 Monotherapy Dose Escalation (Daily Dosing)

The schedule of events for Part 1A are provided in [Table 1](#).

The Part 1A fasting window is defined as: 2 hours predose to 1-hour postdose in general, and ~~C~~ hours predose to 4 hours postdose on days where PK-time matched triplicate ECGs are collected.

~~C~~
I

Table 1 Schedule of Activities: M4076 Monotherapy Dose Escalation (Daily Dosing), Part 1A

Assessments and Procedures	Screen (D -28 to -1)	DLT Period (21 days)					Subsequent 3-week Periods (21 days)			End of Study Intervention Visit	Safety Follow up/ Discontinuation Visit	Notes
Day		1	2	8	9	15	1	8	15	Within 7 days after last dose	30 days after last dose	
Visit Window (days)		-1								+7	+/- 7	Day 1 assessments that could be completed on Day -1 are limited to physical examination, height/weight, and ECOG performance status.
Study Site Visits	X	X	X	X	X	X	X	X	X	X	X	Starting Cycle 4, visits at Day 8 and Day 15 are optional
Written informed consent	X											
Inclusion / Exclusion Criteria	X											
Medical History (includes substance usage); Demography	X											Substances: tobacco use only.
Hepatitis B and C tests	X											To rule out active infection, performed at the Investigator's discretion. See Appendix 6 for details.
Optional HIV Screening	X											HIV testing is optional at the Investigator's discretion unless required locally.

Assessments and Procedures	Screen (D -28 to -1)	DLT Period (21 days)					Subsequent 3-week Periods (21 days)			End of Study Intervention Visit	Safety Follow up/ Discontinuation Visit	Notes
Day		1	2	8	9	15	1	8	15	Within 7 days after last dose	30 days after last dose	
Visit Window (days)		-1								+7	+/- 7	Day 1 assessments that could be completed on Day -1 are limited to physical examination, height/weight, and ECOG performance status.
Serum Pregnancy Test (WOCBP only)	X									X		See Section 8.3.5.
Urine Pregnancy Test (WOCBP only)		X				X						Urine β -hCG results must be available prior to M4076 dosing.
Physical Examination	X	X		X	X	X				X	X	See Section 8.2.1.
Height and Weight	X	X				X				X	X	Collect height at Screening only.
Imaging Disease Assessment (CT/MRI)	X	X (at the end of every 6 weeks for the first 24 weeks, then every 12 weeks)								X		Tumor assessment according to RECIST 1.1 until disease progression, end of study, or death, whichever is earlier. See Section 8.1 for details of imaging.
Vital signs	X	X	X	X	X					X	X	In the first 6 weeks on study treatment, vital signs are measured as follows: 
 • Predose (within approximately 30 to 60 minutes prior) • 4 hours (\pm1 hour) postdose on Day 1 and Day 8. After 6 weeks, vital signs to be measured predose.
Standard 12-lead ECG	X					X post dosing				X	X	
Triplicate digital ECG		X	X	X								See Table 3 for triplicate ECG details.

Assessments and Procedures	Screen (D -28 to -1)	DLT Period (21 days)					Subsequent 3-week Periods (21 days)			End of Study Intervention Visit	Safety Follow up/ Discontinuation Visit	Notes
Day		1	2	8	9	15	1	8	15	Within 7 days after last dose	30 days after last dose	
Visit Window (days)	-1									+7	+/- 7	Day 1 assessments that could be completed on Day -1 are limited to physical examination, height/weight, and ECOG performance status.
ECOG performance status	X	X					X			X	X	See Appendix 10 .
AE, AESI and SAE assessment	Continuous										From time of signing the ICF through the Safety Follow-up Visit, and until completion of the study. SAEs and AESIs should be followed until resolution, stabilization, the event is otherwise explained, or the participant is lost to follow-up (see Section 8.3.3).	
Concomitant medications and procedures (including collection of subsequent anticancer therapy)												
Serum Chemistry	X	X	X	X		X	X	X	X	X	X	For Visit 1/D1, sample can be collected up to 72 hours prior to dosing. D8 and D15 assessments are optional after Week 9. See Appendix 6 for details.
Hematology and Coagulation (PT, aPTT, INR)	X	X	X	X		X	X	X	X	X	X	For Visit 1/D1, sample can be collected up to 72 hours prior to dosing. D8 and D15 assessments are optional after Week 9. See Appendix 6 for details.
Urinalysis	X	X				X	X			X		See Appendix 6 for details.

Assessments and Procedures	Screen (D -28 to -1)	DLT Period (21 days)					Subsequent 3-week Periods (21 days)			End of Study Intervention Visit	Safety Follow up/ Discontinuation Visit	Notes
Day		1	2	8	9	15	1	8	15	Within 7 days after last dose	30 days after last dose	
Visit Window (days)		-1								+7	+/- 7	Day 1 assessments that could be completed on Day -1 are limited to physical examination, height/weight, and ECOG performance status.
Archival tumor biopsy collection	X											If insufficient tissue is available from an archived specimen, or if the biopsy was obtained > 12 months before Screening, a fresh biopsy sample may be requested during screening (prior to D1) unless contraindicated for medical reasons.
Study Intervention Administration												
M4076 Monotherapy		Daily dosing. (Fasting window: 2 hrs predose to 1 hr postdose in general, and 2 hrs predose to 4 hrs postdose on days where PK-time matched triplicate ECGs are collected.)										See additional potential treatment schedules in Appendix 7 .
Pharmacokinetic Assessments												
Blood - PK blood samples M4076		X	X	X	X		X					See Table 3 for PK sample details.
Biomarker Assessments												
		■	■				C C I					

First-in-human Study of M4076 in Advanced Solid Tumors

Assessments and Procedures	Screen (D -28 to -1)	DLT Period (21 days)					Subsequent 3-week Periods (21 days)			End of Study Intervention Visit	Safety Follow up/ Discontinuation Visit	Notes
Day		1	2	8	9	15	1	8	15	Within 7 days after last dose	30 days after last dose	
Visit Window (days)		-1								+7	+/- 7	Day 1 assessments that could be completed on Day -1 are limited to physical examination, height/weight, and ECOG performance status.
Fresh Paired tumor biopsies	X		X									Optional. The first of two paired biopsies should be collected anytime during screening. The second biopsy should be collected on D2 from 2 to 4 hours after study intervention administration. No bone biopsies are allowed. The first biopsy can replace the archival tumor biopsy.
Plasma – Circulating Tumor DNA Sample		X					X			X		Collect predose on dosing days.
Blood – Immuno-phenotyping		X					X D22 only					Collect predose.
Serum/plasma – Circulating factors (cytokines)		X					X D22 only					Collect predose.
CCI												

AE = adverse event; aPTT = activated partial thromboplastin time; β -hCG = beta human chorionic gonadotropin; CT = computed tomography; D = Day; DLT = dose limiting toxicity; ECG = electrocardiogram; ECOG = Eastern Cooperative Oncology Group; γ -H2AX = gamma histone family member X; HIV = human immunodeficiency virus; ICF = informed consent form; INR = international normalized ratio; MRI = magnetic resonance imaging; Pd = pharmacodynamics; PK = pharmacokinetic; PT = prothrombin time; RECIST = Response Evaluation Criteria in Solid Tumors; SAE = serious adverse event; WOCBP = woman of childbearing potential.

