Cytopenia, lymphopenia +/- infections	Refer to Section 6.1 of the M4076 IB.	Exclusion of participants with insufficient bone marrow function. Regular monitoring of laboratory evaluations for hematology and vital signs. Continuous monitoring of AEs with clinical management as indicated, including study intervention interruption, dose modification or discontinuation.
Increased heart rate	Refer to Section 6.1 of the M4076 IB.	Exclusion of subjects with significant cardiac conduction abnormalities. Regular monitoring of ECG and vital signs. Continuous monitoring of adverse events with clinical management as indicated, including study intervention interruption, dose modification or discontinuation.
Birth defects and abortions	In vitro and in vivo genotoxicity investigations showed M4076 to cause genotoxicity. Refer to Section 4.3.3 of M4076 IB.	Strict contraception for participants and their partners as inclusion criteria, during treatment, and thereafter 6 months for females and 3 months for males, including refraining from sperm donations.
Risks associated with drug-drug interactions	No formal drug-drug interaction studies have been conducted with M4076 in humans. Refer to Section 4.2.9 of M4076 IB.	Concomitant administration with strong inhibitors or inducers of CYP3A4 or P-glycoprotein agents is prohibited. Concomitant administration with sensitive clinical substrates of UGT1A1 or P-gp, with potentially narrow therapeutic index or known safety risks are prohibited, specifically irinotecan, digoxin, and oral

		direct thrombin inhibitors. Clinical substrates of CYP3A4 with narrow therapeutic index are prohibited. Clinical sensitive substrates and moderate inhibitors of CYP3A4 should be avoided and if permitted, should be used with caution.
Study Procedures		
Assessment	Summary of Data/Rationale for Risk	Mitigation Strategy
Blood Sampling	Blood sampling is required for participants as detailed in the Schedule of Activities and is considered essential for the study's scientific objectives. Blood sampling carries a risk of AEs including pain, bruising, bleeding, redness and swelling of the site/vein, and infection.	Minimization of blood sampling was thoughtfully considered during protocol development weighing risk to participants versus achievement of the study's scientific objectives.

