Primary	
To determine dose-toxicity relationship and MTD (if reached) of M4076 monotherapy in patients with advanced solid tumors.
 
Endpoints:
 
 Occurrence of Dose Limiting Toxicities (DLTs). Occurrence of adverse events (AEs) and treatment-related AEs. Occurrence of clinically significant changes in vital signs, laboratory parameters, and 12-lead electrocardiogram (ECG) findings. 
Strategy for handling intercurrent events:
 
For DLTs:
 
 Discontinuation of treatment (> 20% planned treatment missed during DLT period) to prevent a DLT: composite strategy (to be considered a DLT). Discontinuation treatment administrations not due to DLT or preventing a DLT (> 20% of planned treatment missed during DLT period): participant not considered in DLT analysis. 
For other endpoints:
 
All available data from participants in safety analysis set will be used.
 
Population:
 
Patients with advanced solid tumors, who are intolerant or have no effective standard therapies available to them.
 
Population level summary:
 
 DLT probability as estimated using BLRM and credibility interval (only applicable for DLTs). Standard summary statistics.
Secondary	
To determine the recommended dose for expansion (RDE) of M4076 monotherapy in participants with advanced solid tumors.
 
 In addition to safety and tolerability, changes from baseline for the following Pd biomarkers may be considered for determining the RDE: ATM pathway readouts such as, but not limited to, p-ATM, γ-H2AX and p-CHK2 in blood and tumor. In addition, pharmacokinetic (PK) data will be used to support determination of the RDE. 
To characterize the PK profile of M4076 monotherapy in participants with advanced solid tumors.
 
 PK parameters of M4076 in plasma after single dose and multiple dose. Urine PK parameters (e.g., renal clearance) will be characterized in Part 1B data permitted.

Objectives	Estimands attributes

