8.2.2 Vital Signs

- Height at screening and weight will be measured and recorded as per timepoints noted in the Schedule of Assessments.
- Oral temperature, pulse rate, respiratory rate, and blood pressure will be assessed.
- Blood pressure and pulse measurements will be assessed in a supine position with a completely automated device. Manual techniques will be used only if an automated device is not available.
- Blood pressure and pulse measurements will be preceded by at least 5 minutes of rest for the participant in a quiet setting without distractions (e.g., television, cell phones).
- Vital signs will be measured in a semi-recumbent position after 5 minutes rest and will include temperature, systolic and diastolic blood pressure, and pulse.

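### Protocol Section 8.2.2 gives two incompatible body positions for the same blood pressure and pulse readings; separately, the vital-signs row of Table 1 should be checked against its own note

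*Protocol*

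**What the plan says.** **Body position.** The third bullet of protocol Section 8.2.2 reads: "Blood pressure and pulse measurements will be assessed in a supine position with a completely automated device". The fifth bullet reads: "Vital signs will be measured in a semi-recumbent position after 5 minutes rest and will include temperature, systolic and diastolic blood pressure, and pulse". Both are current running text.

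**Timing.** In Table 1 (protocol Section 1.3.1) the note beside the vital-signs row opens with "In the first 6 weeks on study treatment, vital signs are measured as follows". It then asks for a predose reading and for a reading 4 hours after dosing on Day 1 and Day 8. It ends with "After 6 weeks, vital signs to be measured predose" and names no visit days for that later time. The site-visit row is marked in every column, with the remark "Starting Cycle 4, visits at Day 8 and Day 15 are optional".

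**Use of the data.** Protocol Section 3, Table 6 lists this among the endpoints of the primary objective: "Occurrence of clinically significant changes in vital signs, laboratory parameters, and 12-lead electrocardiogram (ECG) findings". SAP Section 5 does the same. Protocol Section 9.4.2, Table 17 puts vital signs in its Secondary block. Protocol Section 2.3.1, Table 5 gives this as part of the mitigation for increased heart rate: "Regular monitoring of ECG and vital signs". SAP Section 15.5 summarises baseline, on-treatment maximum and minimum, and the changes from baseline. It also groups the largest changes into categories.

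**The concern.** Pulse and blood pressure are compared with a single baseline reading, which SAP Section 9.2 defines in general as the last non-missing value before first dose. If baseline is taken in one position and a later reading in the other, the change contains a position component as well as any drug effect. The wording allows this between sites and between visits of one participant, and SAP Section 15.5 makes no provision for position.

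Increased heart rate is a named potential risk of M4076, so pulse is a measurement for which an avoidable source of error is unwelcome. Section 8.2.2 is not limited to Part 1A. In Part 1B, SAP Section 15.5 summarises vital signs by dietary status, and a participant measured differently in the two periods would carry the same component into that summary.

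The Table 1 question is of another kind. If the row really is blank after Day 9, the schedule and its note disagree on whether readings are due, and some could be missed. Under the grid alone, the only later scheduled readings would come from the visits after the last dose.

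**Working it through.** No sample size, power or event count is involved, so the check is a comparison of passages.

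**1. Do the two bullets cover the same reading?** Yes. The third bullet of Section 8.2.2 covers blood pressure and pulse. The fifth covers vital signs and lists systolic and diastolic blood pressure and pulse by name. No visit, site or device condition separates the two.

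**2. Does anything hold position constant?** I found no such sentence in Section 8.2.2, in the schedule notes or in SAP Section 15.5. The fourth and fifth bullets ask for 5 minutes of rest, which does not settle position.

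**3. How would position enter the analysis?** Let δ be the difference between the two positions for a given measure.
- Observed change = true change + (position effect at the visit − position effect at baseline).
- With the same position at both, the bracket is zero. With different positions it is +δ or −δ.
- SAP Section 15.5 cuts heart rate and blood pressure changes at 20 and 40 (bpm or mmHg). An observed increase raised by δ is put in a higher category whenever the true increase lies between 20 − δ and 20, or between 40 − δ and 40.
- The same tables split participants by baseline value: heart rate at 100 bpm, systolic pressure at 140 mmHg, diastolic pressure at 90 mmHg. So a between-site difference can move participants across these splits even when each participant is measured consistently.
- The documents give no value for δ. I have not assumed one.

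**4. Table 1, machine-read text.**

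| Row | Columns marked |
|---|---|
| Site visits | Screening; Days 1, 2, 8, 9, 15; Days 1, 8, 15 of later periods; both end visits |
| Vital signs | Screening; Days 1, 2, 8, 9; both end visits |

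Six weeks is 6 × 7 = 42 days, that is, the 21-day DLT period plus one later 21-day period (21 + 21 = 42). The note's first part therefore already reaches into the columns that appear blank, and its second part lies wholly within them.

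**5. Can the blanks be trusted?** Only in part.
- Spanning cells in this table come through as one entry followed by blanks, as in the imaging and daily-dosing rows. A mark spanning Day 9 and the later periods would look exactly like this row.
- Four neighbouring rows (urine pregnancy test, physical examination, height and weight, standard 12-lead ECG) show the same later-period blanks.
- The visit-window entry of −1 sits under Day 1 in one copy of the header and under Screening in a repeat.
- On the other side, the triplicate ECG row falls on Days 1, 2 and 8, which agrees with Table 3. That supports the early columns but says nothing about Day 9 onward.

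**6. Endpoint status.** Table 6 lists DLTs, adverse events, and clinically significant changes in vital signs, laboratory values and ECG under the primary objective. Table 17 has only DLTs under Primary and the rest under Secondary.

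**The case against.** The best defence is that the position conflict is a leftover. The protocol's summary of changes ties the semi-recumbent wording to the design of the eCRF, so the supine bullet may simply have escaped editing, and sites may in practice follow the eCRF. That is plausible and would make the real effect small. It does not remove the conflict, because the supine bullet is still in force and is the more specific instruction for these two measures.

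The analysis is also descriptive, with no hypothesis testing, and heart rate is additionally captured by ECG and analysed in SAP Section 15.6.2. Both points stand and limit the consequence, although ECGs do not replace blood pressure.

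On Table 1 the defence is stronger. A reader might infer that vital-sign monitoring stops between Day 9 and the end of treatment. The documents do not support stating that as fact. The inference rests on cell positions in a table with visible extraction faults, and the note in the same row presupposes later readings. A site would have that note in front of it, and protocol Section 1.3 allows unscheduled assessments.

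**Conclusion.** The position conflict holds on the plain text. It permits inconsistent measurement of pulse and blood pressure, and that can enter the changes from baseline and the on-treatment extremes in SAP Section 15.5. Its size cannot be determined from the documents: δ is not given, and neither is the share of readings taken in each position.

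The disagreement between grid and note in Table 1 is conditional. It is a fault in the plan only if the blanks appear in the source table. Even if they do not, the note names no visit days after week 6, so the row must make them clear.

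Three stronger readings are tempting and are not supported:
- A share of treatment time without readings cannot be given. It would need the blanks to be real, and the estimated 105 days on study are not split into screening, treatment and follow-up.
- It does not follow that sites working from the grid will report smaller maximum changes. Fewer readings can understate an extreme, but nothing shows that any site would ignore the note.
- The dose-escalation result is not put at risk directly. The Bayesian model uses DLTs, and whether vital signs are primary at all differs between Tables 6 and 17.

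**What to change.** 1. **Section 8.2.2.** Reconcile the two bullets to one position, confirmed against the eCRF, and delete the other. Add that this position applies at baseline and at every later reading. This is a text edit of a line or two, with no new procedures.
2. **Table 1.** Check the vital-signs row against the source table. If the blanks are real, reconcile grid and note so that both name the same visits, including how the visits that become optional from Cycle 4 are handled. Which visits to name is for the sponsor to decide. Site visits are already marked in all these columns, so no visit need be added. Any extra measurement work depends on the visits chosen.
3. **Tables 6 and 17.** Give vital signs the same status in both, and carry it into SAP Section 5. The same alignment is needed for the other safety endpoints that Table 17 lists under Secondary.
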